4.2.2.1 Definition

To support the secondary objective assessing the ability of tezepelumab 210 mg SC to prevent asthma exacerbations in adult participants with OCS-dependent asthma while OCS dose reduction, the AAER over 28 weeks and over 52 weeks are calculated.

An asthma exacerbation is defined in Section 1.2.

4.2.2.2 **Derivations**

The start and end date of the asthma exacerbation is collected in the EXACA eCRF form. The asthma exacerbation duration is derived as *Exacerbation end date - Exacerbation start date +1*.

The AAER (in years) over the study treatment period of interest (Week 28 or Week 52) is calculated as the total number of asthma exacerbations over the Week 28 or Week 52 divided by the total time at risk calculated for Week 28 or Week 52, respectively, on the FAS. Derivation of time at risk over 28 or 52 weeks is detailed in two steps.

Derivation of time at risk is presented in Table 5.

Table 5. Time at risk derivation over 28 or 52 weeks

	If a participant attended visit of interest	if visit of interest (Visit 9/Week 28 or
	(Visit 9/Week 28 or Visit 15/EOT Week	Visit 15/EOT Week 52) is not available
	52)	for a participant
Time at	[earliest (date of Visit 9, date of another	[earliest {date of first IP dose + 196 days
risk over 28	biologic initiation) – date of first IP dose	+ 5 days; date of another biologic
weeks	+ 1 – sum of (asthma exacerbations +	initiation, latest(date of last available visit
(years)	7days ^b)] / 365.25	including IPD visit, date of death, date of
		last exacerbation assessment status from
		the EXACD eCRF form)} – date of first
		IP dose + 1 – sum of (asthma
		exacerbations + 7days ^b)] / 365.25
Time at	[earliest (date of Visit 15 ^a , date of last	[{earliest (date of first IP dose + 365 days
risk over 52	exacerbation assessment status from	+ 5 days, date of last exacerbation
weeks	EXACD eCRF form, date of another	assessment status from the EXACD eCRF
(years)	biologic initiation – date of first IP dose +	form, date of another biologic initiation,
	1 – sum of (asthma exacerbations + 7	date of death) – date of first IP dose} + 1
	days ^b)] / 365.25	– sum of (asthma exacerbations + 7
		days ^b)] / 365.25

^a The date of Visit 15 is used irrespective of how late this may have occurred in relation to the protocol schedule.

Two or more exacerbations with the same start date and end date are counted as one exacerbation for the purposes of calculating the number and duration of exacerbations for a participant. In the case that one or more exacerbations are recorded as starting or ending during another exacerbation, these is counted as one exacerbation, using the earliest exacerbation start date and the latest exacerbation stop date to calculate duration.

Additional systemic corticosteroid treatments, emergency room or urgent care visits requiring use of systemic corticosteroids, or inpatient hospitalisation due to asthma occurring during an exacerbation is not regarded as a new exacerbation. To be counted as a new exacerbation it must be preceded by at least 7 days in which neither criterion is fulfilled. If the end date of the first exacerbation or a temporary increase in a stable OCS background dose date, date of ER or urgent care visit, or date of hospital discharge and the start date of the second exacerbation are less than 7 days apart, then these is counted as one exacerbation.

It should be noted that the date of last assessment of exacerbation status from the eCRF might be later than the last available visit during the planned treatment period, in the case that the participant remained in the study with incomplete follow-up options after early discontinuation of IP.

The exacerbations that occur after a participant has discontinued IP but before the end of the time at risk is still accounted when deriving the total number of exacerbations.

^b 7 days should be added to each asthma exacerbation duration as no asthma exacerbation can occur during that time.

Likewise, the time at risk reflects the time at risk regardless of whether the participant is still on IP or not.

Any exacerbations that start within the time at risk but ends after this time point is included in analyses, with the end date adjusted to be no later than the time at risk. Any exacerbation that starts after the time at risk is not included in analyses.

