4.2.13.2 Derivations

The derivation of baseline OCS maintenance dose is defined in Section 3.3.1.2. The OCS dose in mg/day is derived using therapy reasons given in Section 3.3. The percent change from baseline in OCS dose/day is calculated as presented in Section 3.3 on the FAS. Strategies of handling intercurrent events are presented in Section 4.2.

The time (in days) from first IP dose to achieve 50% reduction of OCS dose for the 1st time are calculated as follows:

Time to 50% OCS reduction (days) = (Date of 50% OCS reduction from baseline achieved for the 1^{st} time – date of IP dose) + 1.

If there is no sufficient OCS dose reduction (i.e. percentage OCS dose reduction < 50%) during 28 (or 52) weeks or prior to initiation of another biologic, participants are censored at earliest[date of Visit 9/Week 28 if available or date of first IP dose +196 days if visit not done (or date of the Visit 15/Week 52 if available or date of first IP dose + 364 days if visit not available), date of initiation of another biologic].

The Time to 100% OCS reduction (days) is calculated using the same approach described for the 50% OCS reduction on the FAS.

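### SAP Table 5 ends the 28-week and 52-week time at risk by different rules, so a participant can have more time at risk over 28 weeks than over 52; the effect on the pooled rate is very small

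*SAP*

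**What the plan says.** SAP Section 4.2.2.2 divides total exacerbations by total time at risk. Table 5 has a row for 28 weeks and a row for 52 weeks, and a column for the visit of interest (Visit 9 or Visit 15) attended or not available. EXACD is the eCRF form that dates the last assessment of exacerbation status.

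- **28 weeks, Visit 9 not available.** The cell opens with "earliest {date of first IP dose + 196 days" (plus 5 days). After the date of another biologic it continues "initiation, latest(date of last available visit", then "including IPD visit, date of death, date of" the last EXACD assessment. Last visit, death and last EXACD thus sit together in a latest term, nested inside the outer earliest.
- **52 weeks, Visit 15 not available.** The cell is "earliest (date of first IP dose + 365 days" (plus 5 days), last EXACD, another biologic and death. It has no nested latest and no last-visit term.
- **Visit attended.** The 28-week cell is "earliest (date of Visit 9, date of another" biologic. The 52-week cell takes the earliest of Visit 15, another biologic and also last EXACD.

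The numerator follows the same end date: "Any exacerbation that starts after the time at risk is not included in analyses". Footnote b states "7 days should be added to each asthma exacerbation duration as no asthma exacerbation can occur during that time". Elsewhere the SAP places Week 52 at 364 days: Section 4.2.13.2 censors at "date of first IP dose + 364 days if visit not available", and Section 4.2.4.2 works from Day 364.

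**The concern.** The first 28 weeks lie inside the 52 weeks, so a participant's time at risk over 28 weeks should never exceed that over 52. With different end-date rules in the two rows, it can. An exacerbation that starts between the two end dates is then counted in the 28-week rate and dropped from the 52-week rate.

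The 28-week rule also keeps time running from last contact to death. If an EXACD form is dated after the death, it counts time after death.

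Six secondary rates use this derivation: all exacerbations, those with hospitalisation or ER visit, and those with hospitalisation, each over 28 and 52 weeks (SAP Sections 4.2.2 and 4.2.3). The subgroup repeats use it too, and there one participant weighs more.

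Two smaller slips sit in the same derivation. The 52-week cap uses 365 days where the rest of the SAP uses 364. The 7 days after an exacerbation are subtracted in full even when they run past the end of the period.

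**Working it through.** The documents state no total time at risk and no AAER that depends on Table 5, so there is no figure to reproduce. The check applies the rules literally to assumed dates.

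**Notation.** Day *n* means *n* days after first dose. LV is last available visit including IPD, EX is last EXACD, D is death. No other biologic is started, and exacerbation time is not yet subtracted.

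- T28, Visit 9 not available: min(201, max(LV, D, EX)) + 1
- T28, Visit 9 attended: Visit 9 + 1
- T52, Visit 15 not available: min(370, EX, D) + 1

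**Cases** (Visit 15 missing in all; Visit 9 missing except where stated)

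| Assumed dates | T28 | T52 |
|---|---|---|
| LV = EX = 112, no death | 112 + 1 = 113 | 112 + 1 = 113 |
| LV = EX = 112, D = 150 | 150 + 1 = 151 | 112 + 1 = 113 |
| LV = 84, D = 100, EX dated 110 | 110 + 1 = 111 | 100 + 1 = 101 |
| IPD visit 140, EX = 112 | 140 + 1 = 141 | 112 + 1 = 113 |
| Visit 9 attended at 196, EX = 168 | 196 + 1 = 197 | 168 + 1 = 169 |
| LV = 112, EX = 364 (telephone) | 201 + 1 = 202 | 364 + 1 = 365 |

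The order reverses when EXACD precedes the death or the last visit, or when death precedes a later-dated EXACD. It does not reverse when EXACD falls on or after the last visit and there is no death. In the second case, one exacerbation gives 365.25/151 = 2.42 per year on T28 and 365.25/113 = 3.23 on T52, from the same follow-up.

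**How many participants.** Assume 300 participants, 1% deaths, 12% without Visit 15 and an AAER of 0.8. Only the 300 comes from the documents.

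- EXACD completed at every visit: only deaths before about Week 28 matter. Spread evenly, 300 × 0.01 × 28/52 = 1.6, so 1 to 2 participants.
- EXACD one 4-weekly visit behind the last visit in 25% to 100% of dropouts: simulation (400 trials) gives about 7 to 23 participants with T28 above T52. About 0.4 to 1.3 of roughly 121 events counted at 28 weeks are missing at 52.

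**Effect on the rate.**

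- Deaths only: two participants with 38 extra days each (151 − 113) add 2 × 38/365.25 = 0.21 person-years to about 121/0.8 = 151, or 0.14%.
- Upper end: with 12% dropping out mid-study on average, 52-week person-time is 300 × (1 − 0.12 × 0.5) = 282 years, with 282 × 0.8 ≈ 226 events. Removing 23 × 28/365.25 = 1.76 years and 1.3 events moves the rate from 226/282 = 0.801 to 224.7/280.24 = 0.802.

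**Cap.** 28 × 7 = 196, as in the 28-week cell. 52 × 7 = 364, not 365. The SAP's Table 3 agrees: its target Day 365 for Week 52 counts first dose as Day 1, which is first dose + 364. The slip is one day, and only where the cap is the earliest date.

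**Seven-day tail.** For an exacerbation lasting *d* days, the expected over-subtraction per participant is rate/365.25 × (7*d* + 24.5) days. At a rate of 0.8 this is 0.16 days for *d* = 7 and 0.36 days for *d* = 20, or 0.08% to 0.18% of 196 days. Across rates of 0.5 to 2 per year it is about 0.05% to 0.5%.

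**The case against.** The strongest reply is that the mismatch rarely has effect. The Schedule of Activities (Protocol Section 1.3) has exacerbations assessed at every visit, including IPD and unscheduled visits, and Protocol Section 7.1 collects exacerbation information by telephone after early discontinuation. A last EXACD earlier than the last visit therefore needs a missed form. The SAP itself anticipates the opposite, an EXACD later than the last visit, and that direction gives no reversal. Serious exacerbations before a death may also be known without an EXACD visit, since SAEs are reported within 24 hours of awareness (Protocol Section 8.3.9), so the interval before death is not necessarily blind. The AAER is summarised descriptively and no hypothesis is tested.

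Most of this stands, and it limits the point. A reader might infer that the two rows hold the same dates with the operator reversed. They do not: both cells have an outer earliest, the 28-week latest is capped at day 201 and at another biologic, and the 52-week list omits the last visit. A reader might also infer that dropouts generally lose observed events from the 52-week rate. The visit schedule does not support that. How EXACD is dated depends on the eCRF, which is not among the documents.

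The reply does not explain the different rules. Nothing in the SAP does, and a death before about day 201 without Visit 9 triggers the reversal whenever the last EXACD is not dated on the day of death.

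**Conclusion.** The point holds as an internal inconsistency in a stated derivation. Table 5 permits more time at risk over 28 weeks than over 52, and events between the two end dates count in one rate and not in the other. Deaths after the last EXACD are the firm trigger; a missed EXACD form is a less likely one and can also act through the attended-visit column.

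The size is very small. About 1 to 2 of 300 participants are affected if EXACD is completed at every visit (1% deaths assumed), and the 52-week rate changes by about 0.001 even if every dropout's form lags by one visit. The 365-day cap and the 7-day tail are smaller slips of the same kind. The documents do not support a claim that the pooled AAER or its interpretation would change. The reason to act is that the rule is wrong as written and cheap to correct.

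**What to change.** Use one end-date rule in both rows of Table 5:

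- **Visit attended:** earliest of visit date and another biologic. This removes last EXACD from the 52-week attended cell.
- **Visit not available:** earliest of first dose + 196 + 5 (28 weeks) or first dose + 364 + 5 (52 weeks), another biologic, death, and the later of last available visit (including IPD) and last EXACD.
- Replace 365 by 364, in line with SAP Sections 4.2.4.2 and 4.2.13.2.
- Truncate the 7-day exclusion at the end of the time at risk, as the text below the table already does for the exacerbation end date.
- Delete the sentence above the table that announces two steps; the table has one.

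Under this rule the four reversed cases become 113 and 113, 101 and 101, 141 and 141, and 197 and 197 days. With neither visit available, both rows use the same date *x* apart from the cap, and min(201, *x*) can never exceed min(369, *x*). A grid of 78,652 date combinations (caps 201 and 370, no other biologic) gave no reversal.

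One consequence should be stated in the SAP: an exacerbation that starts after last contact and before death is left out of both rates, unless its report is entered as an EXACD assessment.

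The cost is an edit to one SAP table and its program.

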AAER (all asthma exacerbation and uniquely exacerbations associated with hospitalisation or ER visits, or with hospitalisation only), calculated in years over the study treatment period of interest as the total number of exacerbations in the period of interest divided by the total time at risk of interest. The time during an exacerbation and the 7 days following an exacerbation in which a new exacerbation cannot occur will not be included in the calculation of time at risk for exacerbation. AAER will be summarised descriptively. Any asthma exacerbation that occurs within 7 days of the last date of additional systemic corticosteroids or of a temporary increase in a stable OCS background dose, date of ER or urgent care visit, or date of hospital discharge for a prior asthma exacerbation will be combined and counted as a single

exacerbation event. Further details on combining exacerbation events will be provided in the SAP.

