2 CHANGES TO PROTOCOL PLANNED ANALYSES

No difference with the most recent version of the CSP.

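### Read as a date difference, the exacerbation merge condition in SAP 4.2.2.2 is one day short: it does not merge a second event starting exactly 7 days after the first ends

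*SAP*

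**What the plan says.** SAP 4.2.2.2 treats the counting of exacerbations in two consecutive sentences. The first sets a requirement for a new event: "To be counted as a new exacerbation it must be preceded by at least 7 days in which neither criterion is fulfilled". The second gives the condition for merging. It compares the second event's start date with one of several anchor dates (end of the first exacerbation, date of a temporary OCS increase, ER or urgent care visit, hospital discharge) and ends "and the start date of the second exacerbation are less than 7 days apart, then these is counted as one exacerbation".

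For the denominator, duration is defined as "Exacerbation end date - Exacerbation start date +1", and footnote b to Table 5 says "7 days should be added to each asthma exacerbation duration as no asthma exacerbation can occur during that time".

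Protocol 9.4.3.2 combines with the prior event "Any asthma exacerbation that occurs within 7 days of the last date of additional systemic corticosteroids" or of the other anchor dates. On time at risk it says "The time during an exacerbation and the 7 days following an exacerbation in which a new exacerbation cannot occur will not be included". It leaves further detail on combining events to the SAP. SAP Section 2 states "No difference with the most recent version of the CSP".

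**The concern.** The merge sentence is the only one of the SAP's counting statements that compares two recorded dates against a threshold, so it is the one a programmer is most likely to code. Subtracting the dates and applying a strict inequality at 7 leaves a second event on E+7 unmerged. Every other statement on the subject puts E+7 inside the first event's window.

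The numerator and denominator of the AAER would then follow different rules on that day: an event is counted on a day already taken out of time at risk because no event is supposed to be possible there. The count feeds the AAER and its exact Poisson interval, the table of exacerbations per participant, the hospitalisation/ER and hospitalisation-only rates (SAP 4.2.3, derived in the same way), and their subgroup repeats.

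**Working it through.** The plan states no exacerbation count or rate, so there is no figure to reproduce. The check is of the boundary, followed by a sensitivity calculation.

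**Step 1: the boundary.** Let E be the end date of the first event, S the start date of the second, and g = S − E. The number of free days between them is g − 1.

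- Preceding SAP sentence: new only if g − 1 ≥ 7, that is g ≥ 8.
- Protocol 9.4.3.2: merged if g ≤ 7.
- Time at risk: duration includes both end dates, so the 7 added days are E+1 to E+7. S lies in removed time if g ≤ 7.
- SAP merge sentence as a date difference: merged if g < 7.

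| g | Free days | Preceding SAP sentence | Protocol | S in removed time? | Merge sentence, date difference |
|---|---|---|---|---|---|
| 6 | 5 | not new | merged | yes | merged |
| 7 | 6 | not new | merged | yes | **not merged** |
| 8 | 7 | may be new | new | no | not merged |

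The mismatch is one day wide, at g = 7.

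**Step 2: one participant, assumed dates.** Events on study days 50–59 and 66–75 give g = 66 − 59 = 7. Visit 9 is on day 197.

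- Kept separate: days subtracted = (10 + 7) + (10 + 7) = 34. Time at risk = 197 − 34 = 163 days. Rate = 2 × 365.25 / 163 = 4.48 per year.
- Merged (days 50–75): days subtracted = 26 + 7 = 33. Time at risk = 197 − 33 = 164 days. Rate = 1 × 365.25 / 164 = 2.23 per year.

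Over 52 weeks, with Visit 15 on day 365, the figures are 2 events in 331 days (2.21 per year) against 1 event in 332 days (1.10 per year). When the events are kept separate, day 66 is subtracted twice, once as the seventh day after the first event and once as the first day of the second. That is why 34 days are subtracted for 33 distinct days. This shows the mechanism for one participant, not a study-level effect.

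**Step 3: study-level size, on assumed inputs.** Expected starts on E+7 = number of exacerbations × hazard multiple / 365.25, with a background rate of 1 per year.

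- Low: 150 × 1 / 365.25 = 0.4 events. Share of events = 1 / 365.25 = 0.3%.
- High: 350 × 5 / 365.25 = 4.8 events. Share of events = 5 / 365.25 = 1.4%.

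A second calculation assumed 300 participants, 52 weeks, 10-day events, a constant hazard and an AAER of 0.5 to 2 per year. It puts 0.14% to 0.55% of events on the boundary and raises the AAER by about 0.1% to 0.6%. If 1% to 5% of events are simply supposed to fall there, the AAER rises by about 1% to 5%. Nothing in the documents points to such a share.

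**Step 4: after the change.** With merging at g ≤ 7, all four rules agree: g ≤ 7 is one event, and g ≥ 8 is a new one.

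**The case against.** The best defence is that the SAP never says events are merged *only* under the strict inequality. The merge sentence gives a sufficient condition and says nothing about g = 7. The sentence before it is mandatory, and a start on E+7, with 6 free days, fails it. Taken together, the two sentences do not make E+7 a new event, which agrees with the protocol and footnote b. Alternatively, the distance in the merge sentence can be read as full days lying between the two dates, which makes it the exact complement of the preceding sentence. The SAP amendment history supports agreement as the intent: it records the sentence as a clarification of the counting rules, in line with the protocol.

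Most of this stands. A reader might infer that the SAP contradicts itself and yields two different counts from the same data, or that it knowingly departs from the protocol and makes Section 2 untrue. The text does not compel either conclusion.

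What the defence does not remove is the risk in programming. The SAP does not say that intervening days are to be counted, and a sentence setting an end date against a start date invites plain subtraction. Coded that way and on its own, it gives a result that the protocol excludes.

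The objection on size is also fair. The AAER is descriptive and no hypothesis is tested. At 150 to 350 events the Poisson interval is roughly ±1.96/√150 = 16% to ±1.96/√350 = 10%, far wider than the effect in step 3.

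**Conclusion.** The point holds as a wording error at one boundary day. Taken as a date difference, the stated threshold leaves E+7 unmerged, while the neighbouring SAP sentence, footnote b and Protocol 9.4.3.2 all assign E+7 to the first event. A literal program would count an event in time that the denominator excludes.

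The effect is small: about 0.4 to 5 events, or 0.3% to 1.4% of the AAER. That range rests on the assumed 150 to 350 exacerbations and the assumed hazard on E+7, since the documents supply neither. A reader might infer from the participant example that reported rates could be materially inflated. That example concerns a single gap of exactly 7 days and does not carry over to the study.

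The primary endpoints do not use the count. The exacerbation-free proportions do not change either, because a participant with a second event on E+7 has already had the first.

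**What to change.** In SAP 4.2.2.2, keep the listed anchor dates and replace the strict threshold in the merge sentence with: *are 7 days apart or less (second start date minus that date <= 7)*. The merge sentence, the 7-free-days sentence, footnote b to Table 5 and Protocol 9.4.3.2 then give the same count, and the statement in SAP Section 2 needs no change on this point.

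The cost is one SAP sentence and one condition in the program. No new data are needed.

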4.2.2.3 Handling of Dropouts and Missing Data

No data imputation.

4.2.2.4 Primary Analysis of Secondary Endpoint

Number and percentages of participants with at least one exacerbation as well as with specific number of exacerbations (0, 1, etc.) is presented. The number of exacerbations per participant as well as total days of exacerbations and total days of exacerbations per participant is be presented.

The total number of exacerbations, total time at risk (years) and AAER estimated as defined in Section 4.2.2.2 are presented over 28 and over 52 weeks. In addition, 95% confidence interval is calculated based on exact Poisson confidence interval.

The summaries are presented be based on the FAS.

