5.1 Inclusion Criteria

Participants are eligible to be included in the study only if all of the following criteria apply:

Age

1 Participant must be 18 to 80 years of age inclusive, at the time of signing the informed consent.

Type of Participant and Disease Characteristics

- History of physician diagnosed asthma that requires continuous treatment with high-dose ICS (high-dose ICS is the highest approved dose in a country; see Appendix I) plus a LABA for at least 6 months prior to Visit 1 (to be documented in medical records). The ICS and LABA can be contained within a combination product or given by separate inhalers:
 - (a) For ICS/LABA combination preparations, the highest approved maintenance dose in the local country will meet this ICS criterion.

Note: Additional maintenance asthma controller medications (eg, LTRAs, tiotropium, cromone, theophylline) are allowed (see Table 5).

- 3 Long-term OCS therapy for asthma, equivalent to a daily dose of at least 5 mg and up to 40 mg of prednisone/prednisolone for at least 3 continuous months directly preceding Visit 1 (to be documented in medical records).
 - Note: Alternate intake of OCS (ie, every other day) or other frequency is allowed provided the average daily dose is equivalent to at least 5 mg of prednisone/prednisolone and the participant is switched to a daily intake of prednisone/prednisolone at Visit 1. Systemic corticosteroid doses administered by any route other than oral cannot be used to determine the average daily dose preceding Visit 1.
- 4 Participant should be on a stable maintenance OCS dose for at least 4 weeks prior to Visit 1. If taking a type of OCS other than prednisone/prednisolone at Visit 1, then the participant must agree to switch to prednisone/prednisolone as their OCS by Visit 2 and for the duration of the study.

- Documented history of at least 1 asthma exacerbation event within 12 months prior to Visit 1. An asthma exacerbation will be defined as a worsening of asthma symptoms that leads to any of the following:
 - (a) A temporary bolus/burst of systemic corticosteroids (or a temporary increase in stable OCS background dose) for at least 3 consecutive days to treat symptoms of asthma worsening; a single depo-injectable dose of corticosteroids will be considered equivalent to a 3-day bolus/burst of systemic corticosteroids

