Subgroup analyses are performed on the FAS. If any of the subgroups have fewer than 10 participants in a level, then this subgroup level is not included in any model. If that leaves only one subgroup level, the analysis is not performed for that categorical variable.

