4.2.2.6 Subgroup Analyses of Secondary Endpoint

The analysis described in Section 4.2.2.4 is repeated in subgroups described in Section 4.2.1.7.

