4.2.3.4 Primary Analysis of Secondary Endpoint

The same analysis as described in Section 4.2.2.4 is presented but including exacerbations associated with hospitalisation or emergency room (ER) or with hospitalisation only. The analyses are performed based on the FAS.

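### The exact Poisson interval for the all-exacerbation AAER leaves out variation in rates between participants and is too narrow for the patient population unless events are sparse

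*SAP*

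**What the plan says.** SAP 4.2.2.2 defines the AAER as a pooled ratio, "calculated as the total number of asthma exacerbations over the Week 28 or Week 52 divided by the total time at risk". SAP 4.2.2.4 then adds the interval: "In addition, 95% confidence interval is calculated based on exact Poisson confidence interval". SAP 4.2.2.5 plans no additional analysis, so this is the only interval for the AAER.

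The method carries over to the subgroups (SAP 4.2.2.6: "The analysis described in Section 4.2.2.4 is repeated in subgroups described in Section 4.2.1.7") and, through SAP 4.2.3.4 and 4.2.3.6, to the rates of exacerbations with hospitalisation or ER visit and with hospitalisation only.

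The objective in SAP 4.2.2.1 is to assess "the ability of tezepelumab 210 mg SC to prevent asthma exacerbations in adult participants with OCS-dependent asthma". The endpoint table in SAP 4.2 lists the AAER and its 95% CI in the population-level summary column. Protocol 9.4.3.2 says only that the AAER is summarised descriptively and names no interval. Neither document plans a negative binomial model, scale factor, robust variance or bootstrap for this endpoint.

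**The concern.** An exact Poisson interval on a pooled count assumes that the variance of the total equals its mean. If participants are regarded as a sample and their underlying rates differ, the variance is larger.

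The plan gives no ground for assuming equal rates. Entry requires "Documented history of at least 1 asthma exacerbation event within 12 months prior to Visit 1" with no upper limit, and baseline OCS may be anywhere from 5 to 40 mg/day. Protocol 4.2 links eosinophilic asthma to recurrent exacerbations, while enrolment deliberately mixes eosinophil levels. The 7-day rule merges neighbouring events and shortens time at risk, but it does not deal with differences between participants.

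No hypothesis is tested, so the interval is the plan's formal statement of uncertainty about the AAER. If it is too narrow, the report claims more precision than the data give, overall and in the larger subgroup levels. The other planned intervals do not share this weakness. The Clopper-Pearson proportions count each participant once, and the repeated-measures models allow for correlation within participant.

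**Working it through.** **Plan's own figure.** The only precision figure is the Clopper-Pearson half-width for the primary proportions (SAP 1.3). Beta quantiles for 150 of 300 give ±5.80 points, matching the stated ±5.8. There is no corresponding figure for the AAER.

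**Inputs.** From the documents: N about 300; follow-up of 28 weeks (196/365.25 = 0.537 years) and 52 weeks (364/365.25 = 0.997 years). Assumed: the AAER, and the dispersion k of a gamma-Poisson model. Every simulated participant has full follow-up.

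**Formulas.** With D events in T years:
- exact Poisson limits: χ²(0.025; 2D)/2T and χ²(0.975; 2D+2)/2T
- variance with differing rates: Var(D) = E(D)(1 + kμ), where μ is expected events per participant
- robust interval: r = D/T, SE(r) = √[N/(N−1) · Σ(yᵢ − r·tᵢ)²]/T, limits r·exp(±1.96·SE/r)

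**Example.** 240 events in 300 person-years, so r = μ = 0.80. The exact Poisson interval is 0.70 to 0.91. Allowing for dispersion, the limits are 0.80·exp(±1.96·√[(1 + 0.8k)/240]):

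| k | 1 + 0.8k | SE ratio | 95% CI |
|---|---|---|---|
| 0.5 | 1.4 | 1.18 | 0.69 to 0.93 |
| 1 | 1.8 | 1.34 | 0.68 to 0.95 |
| 2 | 2.6 | 1.61 | 0.65 to 0.98 |

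**Coverage of the nominal 95% exact Poisson interval** (N = 300, 20,000 simulated trials per cell):

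| AAER/year | Weeks | k = 0 | k = 0.5 | k = 1 | k = 2 |
|---|---|---|---|---|---|
| 0.1 | 52 | 95.5% | 94.9% | 94.6% | 93.8% |
| 0.3 | 52 | 95.3% | 94.2% | 91.9% | 88.6% |
| 0.5 | 52 | 95.7% | 92.4% | 89.5% | 84.1% |
| 1.0 | 52 | 95.2% | 89.4% | 83.7% | 74.7% |
| 1.5 | 52 | 95.2% | 86.7% | 78.8% | 68.1% |
| 0.5 | 28 | 96.2% | 94.6% | 93.3% | 90.4% |
| 1.0 | 28 | 94.7% | 92.1% | 89.1% | 83.2% |

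The approximation 2Φ(1.96/√(1 + kμ)) − 1 agrees. At AAER 1.0 over 52 weeks it gives about 89%, 83% and 74% for k = 0.5, 1 and 2. The robust interval covered 94.3% to 95.4% in all N = 300 scenarios.

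A separate grid at AAER 0.5, 0.8 and 1.2, taking 52 weeks as one year and k = 0.5 to 2, gave 92.7% down to 71.8% at 52 weeks and 94.9% down to 81.0% at 28 weeks.

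**Where the problem stops.**
- Rates held fixed for the enrolled participants (mean 0.8/year, 52 weeks): 95.0% to 95.5%. The interval is right for that narrower target.
- Low dispersion, AAER 0.5 to 1.2, 52 weeks: 94.0% to 94.9% at k = 0.1 and 92.4% to 94.2% at k = 0.25.
- Rare rates of 0.05 to 0.1/year with k = 0.5 to 2: 93.3% to 96.8% at N = 300 and 96.5% to 98.8% at N = 50.

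**Small levels.** At N = 30, 52 weeks and k = 1, exact Poisson covers 84.9% at AAER 1.0 against 93.9% for the robust interval. At 0.05/year the order reverses: 97.8% against 70.9%, with zero-event samples counted as misses for the robust interval. Using the robust interval at 10 or more events and exact Poisson below gave 94.4% to 95.5% at N = 300, 92.5% to 98.8% at N = 50 and 90.6% to 99.0% at N = 30, over rates 0.05 to 1.2 and both periods.

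**The case against.** The strongest reply is that the size is wholly assumed. The eligibility criteria show that rates may differ, not by how much, and at dispersion of 0.25 or less the loss is under 3 points. The 72% is a single corner (AAER 1.2, dispersion 2, 52 weeks). That stands as a limit on the size. It does not defend the method, because the robust interval needs no dispersion value and covers correctly at k = 0 too.

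Secondly, the AAER is a descriptive secondary endpoint in a single-arm trial, and the precision-based sample size concerns only the primary proportions. This also stands and limits the weight of the point: no decision or error rate hangs on the interval. But the SAP chose to report a 95% interval, and it should mean what it says.

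Thirdly, SAP 4.2.2.4 tabulates participants by number of exacerbations, so overdispersion will be visible to a reader. True, but those counts do not enter the interval.

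Finally, an event-count rule can put two interval types in one subgroup table, and coverage at N = 30 may still fall to about 91%. Both are real costs. Even so, at N = 30 exact Poisson does worse where dispersion matters, and the robust interval alone fails when events are few.

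**Conclusion.** The concern holds for the all-exacerbation AAER, in the FAS and in subgroup levels with enough events, when the interval is read as a statement about the patient population. The direction is certain if rates vary between participants. The size depends on assumed values: negligible at dispersion near 0.1, and for dispersion 0.5 to 2 at AAER 0.5 to 1.2 a standard error too small by a factor of 1.12 (√(1 + 0.5×0.5)) to 1.84 (√(1 + 2×1.2)) over 52 weeks. It does not extend to rare rates or sparse levels, where exact Poisson is about right or conservative. The point estimate and the primary endpoints are unaffected. This should be changed, but it does not threaten the trial's main conclusions.

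**What to change.** In SAP 4.2.2.4, keep the crude rate and compute its 95% interval from participant-level variance, either robust or by a bootstrap that resamples participants. Pre-specify a minimum event count below which the exact Poisson interval is used, including levels with no events; 10 is a workable cut-off. Apply the same rule by reference in 4.2.2.6, 4.2.3.4 and 4.2.3.6.

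The existing rule in 4.2.1.7 ("If any of the subgroups have fewer than 10 participants in a level, then this subgroup level is not included in any model") cannot stand in for this, since it counts participants rather than events and applies only to models.

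Where events are not sparse, an intercept-only negative binomial model with log time at risk as offset is an alternative, though its estimate need not equal the crude rate when time at risk differs between participants.

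The cost is one or two SAP sentences, standard SAS code and a footnote saying which interval each row uses. Intervals widen by about 1.2 to 1.6 times at AAER 0.8 over 52 weeks for dispersion 0.5 to 2, and hardly at all if dispersion is near zero. Point estimates do not change if the crude rate is kept.
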